240 subjects are expected to be required for this trial. From 0 to 28 days after birth, infants who had signed informed consent by a guardian were screened. Guardian according to their own will choose to attend breastfeeding group or artificial feeding group (mother for subjective and objective reasons for exclusive breastfeeding, can choose to join artificial feeding group, the researchers shall not interfere in the decision of the guardian or guide), breast feeding group and artificial feeding group subjects of 80 cases and 160 cases, respectively.160 subjects in the artificial feeding group were randomly assigned to the experimental group and the control group in a ratio of 1:1 ratio. The experimental formula and control formula were used for artificial feeding or mixed feeding. Artificial feeding was conducted no less than 2 times a day at 0 to 4 months and no less than 5 times a day at 4 to 12 months. Infants in the breastfeeding group need to be breastfed or mixed fed, exclusively breastfeeding daily at 0 to 4 months of age (must be fully breastfed 1 day before the visit), and breastfeeding at least once a day at 4 to 12 months of age.

From the perspective of ethical and subject protection, if the infant and guardian

are eligible and willing to breastfeeding, we will assign the subject to the breastfed group, rather than against the wishes of the parent. If the parent / legal guardian is unable to breastfeed exclusively for objective reasons, or clearly and strongly willing not to breast, these infants will be randomized to the trial or the control group. It should be noted that during the decision-making process, the investigator should encourage the parents / guardian to breastfeeding the infant; rather than interfering or guiding the decision-making process to induce the test infant to participate in the artificial feeding group.

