6.1 Test flow chart

6.2 recruit

The investigator will identify suitable infants, contact their parents or guardians by telephone and otherwise, and make an appointment for informed consent and subject screening.

6.3 informed consent

The subject's guardian must personally sign the informed consent form and date before conducting any trial process. If the version is updated, contact the guardian to sign the latest version of the informed consent.

A written version of the informed consent was provided to the guardian of the subject, and the investigator should explain the following: the nature of the trial; the content of the subject; the requirements of the protocol; known side effects and any risks involved in participation. The guardian should also be clearly informed that the baby can be withdrawn from the study at any time for any reason, without affecting the baby's medical treatment, legal rights, and no obligation to provide a reason for the withdrawal.

The guardian of the subject was allowed enough time to consider the relevant information and the opportunity to ask the researcher, their GP or other independent party to decide whether to enroll the infant in the trial. The subject's guardian will then sign and date the informed consent form, followed by the investigator giving the informed consent. The investigator who gave the informed consent must have the appropriate qualifications and experience and must be authorized by the principal investigator at each institution. A copy of the signed informed consent form will be given to the subject's guardian for retention and the original remains at the study institution.

6.4 dressing by screening

The investigator will ask the guardian, investigate the basic information of the subject infant, fill in the screening record and the Subject Screening and Enrollment Registration Form, and the infant will be included in the study after meeting the inclusion and exclusion criteria. If the guardian chooses to exclusively breastfeed the infant, the infant will be assigned to the breastfeeding group; if due chooses artificial or mixed feeding, the infant will be randomized to the trial or control group.

6.5 randomization

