6.6 Interview

6.6.1 Visit 1

Visit 1 will be performed on the 28th day of life and the investigator will obtain the following information:

· Mode of delivery;

· Pregnancy-related complications;

· Parents' physical condition (height, weight, medical history);

· Parents' living habits (smoking history, drinking history, exercise habits);

· Parents' social and economic background (education level, employment status);

· Growth and development parameters (height, head circumference, chest circumference, body weight);

- Stool samples (16S rRNA, SCFAs, sIgA);
- · Gastrointestinal comfort survey and questionnaire;
- · Questionnaire on baby crying condition;
- · Questionnaire on infant diarrhea;
- · Questionnaire on upper respiratory tract infection in infants;

⁵⁷Steenhout P, Sperisen P, Martin F, et al.Term Infant Formula Supplemented with Human Milk Oligosaccharides (2' Fucosyllactose and Lacto - N - neotetraose) Shifts Stool Microbiota and Metabolic Signatures Closer to that of Breastfed Infants[J].The FASEB Journal, 2016, 30.

- · The Bristol Stool Classification Questionnaire;
- · Past medical history and current medical history.

6.6.2 Visit 2

Visit 2 will be conducted on Birth Day 90 with a window of 3 days and the investigator will measure and obtain the following information:

· Growth and development parameters (height, head circumference, chest circumference, body weight);

- · Gastrointestinal comfort survey and questionnaire;
- · Questionnaire on baby crying condition;
- · Questionnaire on infant diarrhea;
- · Questionnaire on upper respiratory tract infection in infants;
- · The Bristol Stool Classification Questionnaire;
- · Adverse events and serious adverse events.

6.6.3 Visit 3

Visit 3 will be conducted on Post Birth Day 180 with a window of 5 days and the investigator will measure and obtain the following information:

· Growth and development parameters (height, head circumference, chest circumference, body weight);

- Blood samples (hsCRP, analysis of lymphocyte subsets, amino acids, osteocalcin, alkaline phosphatase, albumin);
- Stool samples (16S rRNA, SCFAs, sIgA);
- · Gastrointestinal comfort survey and questionnaire;
- · Questionnaire on baby crying condition;
- · Questionnaire on infant diarrhea;
- · Questionnaire on upper respiratory tract infection in infants;
- · The Bristol Stool Classification Questionnaire;
- · Adverse events and serious adverse events.

6.6.4 Visit 4

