9.7.1 Main endpoint indicators

Primary endpoint index: Changes in the intestinal flora of infants compared between the test group and the control group.

9.7.2 statistical analysis technique

16 The lowest ranked taxon O TUs was obtained from sequencing data for further analysis.

(1) Analysis of the bacterial species diversity profile

• The diluability curve (Rarefaction curve) is used to analyze whether the existing OTU data can reflect the diversity of the sample flora, and the sequencing depth is used to evaluate whether the sequencing data amount of the sample is reasonable. Random sampling of sequences is used to construct the number of sequences drawn and the number of OTU they can represent. When the curve is flat, it indicates that the amount of sequencing data is reasonable.

• Species composition analysis was conducted, and according to the species information and abundance information of O TUs, the appropriate taxonomic level (species <genus <family <order <class <phyla) was selected to draw the colony columns of different groups of samples.

• The Alpha Diversity (Alpha diversity) index was used to quantify the bacterial community characteristics of the samples, as described by the S obs, C hao, Ace, Shannon, and S impson index. The S obs Index, Chao, index and Ace index can estimate the number of species in the sample, and the Shannon index and S impson index reflect the species richness and species uniformity of the sample.

(2) Analysis of microflora composition differences among samples

• Differences in species composition between different groups were analyzed using W ilcoxon (comparing two groups) and K ruskal-Wallis (three groups and above) to compare differences in Alpha diversity index between groups, if P < 0.05.

• Beta diversity (Beta diversity) analysis was used to use the species composition or evolutionary relationship between species and abundance information to calculate the inter-sample distance, and the similarity or difference of community composition between different grouped samples was explored. The results are shown in Heatmap diagram.

• Using p rincipal component analysis (p rincipal component analysis, PCA) to assess whether infant samples from different groups can be distinguished. When the sample composition is more similar, the closer the distance reflected in the PCA plot is. Samples from different backgrounds may exhibit a distribution of dispersion and aggregation.

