• Using W ilcoxon and K ruskal-Wallis tests by LEfSe software to identify significantly different species between groups and visually show the distribution of different species between groups at each taxonomic level.

(3) Association analysis of environmental factors

• Correlation analysis was used to explore the associations between infant gut microbiota and environmental factors (sex, birth weight, etc.) in different groups. Correlation coefficients were calculated using P earson and S pearman when samples cannot satisfy a continuous normal distribution and a linear relationship. The results are presented as the Heatmap plots.

10 Management plan for common / serious adverse events

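### The randomised test-control comparison is tested without adjustment, although mode of delivery is collected and could be used to gain precision

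*Protocol*

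**What the plan says.** Protocol section 9.7.1 defines the primary comparison as "Changes in the intestinal flora of infants compared between the test group and the control group", which is the randomised contrast. Section 9.7.2(2) says that differences between groups are "analyzed using W ilcoxon (comparing two groups) and K ruskal-Wallis (three groups and above"), and that these tests serve "to compare differences in Alpha diversity index between groups, if P < 0.05". At taxon level the same two tests are run: "tests by LEfSe software to identify significantly different species between groups". None of these carries a covariate or a stratum.

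Section 6.5.1 describes block randomisation and names no stratification factor. Section 6.6.1 lists "Mode of delivery" among the Visit 1 items. Section 9.3 admits an infant to the full analysis set on completing Visit 1, so the item should be available for that whole set.

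Other factors enter only in section 9.7.2(3), which correlates "associations between infant gut microbiota and environmental factors (sex, birth weight, etc.) in different groups" and shows the result as a heatmap. That does not adjust the test-control contrast.

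On feeding, section 4 states: "The experimental formula and control formula were used for artificial feeding or mixed feeding". Section 6.4 says that if the guardian chooses "artificial or mixed feeding, the infant will be randomized to the trial or control group". The choice therefore comes before allocation.

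**The concern.** A factor fixed before randomisation and related to the outcome can be used in two ways: the design can balance it, or the analysis can adjust for it. The protocol names neither for the primary contrast. By planning to correlate flora with factors such as sex and birth weight, it shows that it expects such relations to exist.

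Without adjustment, variance that a known factor could explain stays in the error term and lowers power. If the arms happen to differ on that factor, the estimate in the trial actually run is shifted and nothing corrects it. With about 64 evaluable infants per arm, neither effect is negligible if the factor is prognostic. For mode of delivery the remedy needs no new data.

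**Working it through.** **Inputs from the protocol.** Section 6.5.2 gives 80 infants per group and 20% loss; section 9.7.2(2) gives a significance level of 0.05. Sidedness is not stated, so two-sided is assumed. No effect size, SD or power is given.

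**The plan's own figure.** 80 × (1 − 0.20) = 64 per group, which reproduces.

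**Assumptions.** Prevalence of the binary factor 30% to 50%; share of outcome variance explained (R²) 0% to 20%; effect 0.5 SD.

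**1. Chance imbalance.** The standard error of the difference in prevalence between arms is √(2p(1−p)/n).
- p = 0.3, n = 64: √(2 × 0.21/64) = 0.081; P(difference above 10 points) = 0.217.
- p = 0.4, n = 64: √(2 × 0.24/64) = 0.087; probability 0.248.
- p = 0.5, n = 64: √(2 × 0.25/64) = 0.088; probability 0.258.
- With all 80 per arm, the probabilities are 0.168 to 0.206.

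**2. What a 10-point imbalance does.** A factor with 50% prevalence that explains R² has coefficient √R²/0.5 in SD units. For R² of 5%, 10% and 20% this is 0.447, 0.632 and 0.894. A 10-point imbalance moves the test-control difference by a tenth of that: 0.045, 0.063 or 0.089 SD. The standard error of the difference is about √(2/64) = 0.177 SD, so the largest of these shifts is about half a standard error.

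**3. Precision by formula.** Adjustment multiplies the residual variance by (1 − R²), so it is worth n/(1 − R²) infants per arm: 64/0.95 = 67, 64/0.90 = 71 and 64/0.80 = 80. With the Wilcoxon efficiency of 3/π, the difference detectable at 80% power is 2.80 × √(2/64)/√(3/π) = 0.507 SD. At that difference, power becomes 82.0%, 84.0% and 87.9%.

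**4. Precision by simulation.** The settings were 64 per arm, normal outcome, two binary baseline factors at 50% prevalence jointly explaining R², and 4,000 trials per setting. Plain Wilcoxon was compared with a linear model on ranks containing both factors, at an effect of 0.5 SD.

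| R² | Wilcoxon | Adjusted |
|---|---|---|
| 0% | 77.5% | 76.9% |
| 5% | 77.3% | 78.6% |
| 10% | 77.4% | 81.3% |
| 20% | 77.7% | 85.3% |

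The Monte Carlo standard error is about √(0.78 × 0.22/4000) = 0.7 points, so the gap at R² = 0 is noise. With no true effect, both methods rejected in about 4% to 6% of trials.

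**5. Which covariates are available before allocation.** Mode of delivery is fixed at birth, so recording it at day 28 does no harm. For artificial versus mixed feeding, section 6.4 describes the choice but shows no field that stores it; the screening record is said to hold only basic information. In the section 1 schedule (a broken table), the feeding questionnaire has four ticks, which fit Visits 1 to 4 and not screening. Infants enter at 0 to 28 days. The intervention is 360 days in section 1 and 332 days from day 28 in section 4 (360 − 28 = 332). It is therefore unsettled whether Visit 1 comes before or after study formula starts.

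**The case against.** The strongest reply is that nothing here is an error. Randomisation makes the unadjusted Wilcoxon test valid, and its 5% error rate already allows for chance imbalance; the simulation agrees. A reader might infer that the primary test is biased or can produce false positives beyond its level. The documents do not support that. The loss is one of efficiency and of conditional imbalance, and this part of the objection stands in full.

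A reader might also infer that feeding mode is recorded before allocation for every infant and can be adjusted for at once. No such field is shown, and the Visit 1 questionnaire may describe feeding that began after allocation.

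A third tempting reading is that mixed-fed infants on only two formula feeds a day blur the whole comparison. Stool is taken at days 28, 180 and 360. The two-feed minimum applies to 4 months, so it covers only the day-28 sample; the later two fall under the minimum of five feeds.

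Further, the protocol gives no evidence that mode of delivery is prognostic for flora, and no R². Section 4 calls the trial exploratory, and section 9.2 treats inference as for reference only. These points limit the size of the concern. They do not remove it: a trial that leans on description depends on the precision of its estimates. Although covariates are often left to an analysis plan, this protocol itself names the tests and leaves the covariate out.

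**Conclusion.** The point holds as an improvement in efficiency, not as a flaw in validity. The stated method leaves unused a baseline factor that the trial collects. At 64 per arm, the gain at 0.5 SD is about 1 point of power if the covariates explain 5% of variance, 4 points at 10% and 8 points at 20%, equivalent to 67, 71 or 80 infants per arm. At R² = 0 there is no gain and essentially no loss. If mode of delivery is the only usable covariate, the R² to read is what it explains alone. Prevalence, R² and effect size are all assumptions. No power target is stated, so none is missed.

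**What to change.** - For each alpha-diversity index and each SCFA, make the main test-control result a linear model on the rank or log scale adjusted for mode of delivery, or a van Elteren test stratified by it. Report the adjusted difference with its 95% confidence interval where the model gives one.
- Keep the plain Wilcoxon test as a sensitivity analysis.
- Add artificial versus mixed feeding only where the guardian's choice was documented before allocation, for example on the screening record. Do not substitute the Visit 1 feeding questionnaire, which may be post-randomisation.
- Centre may be added if the number of centres, which the protocol does not give, is small.

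The cost is a few degrees of freedom out of about 128 infants (2 × 64), a change of wording, some analysis code and possibly one field on the screening form. Mode of delivery alone needs no new data.

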10.1 Common adverse events / serious adverse events

The test and control milk powder contain lactose and milk protein, and some infants may have symptoms of lactose intolerance or milk protein allergy. Lactose intolerant populations were excluded at screening to maximize potential hazards. Trial and control milk powder generally do not result in the occurrence of serious adverse events.

10.2 Management of the adverse events

An adverse event is an adverse event after a patient or a clinical study subject receives an investigational product that does not necessarily be causally related to the trial. Adverse events are laboratory findings of disease, signs or symptoms, and / or abnormalities during the course of the study. Adverse events include subjects in contacting the investigator or their personal physician, being examined or given medical guidance. This may or may not cause the subject's withdrawal from the study. Adverse events are generally classified as serious or not serious.

All adverse events during the study should be reported and recorded, regardless of whether they are considered serious or not serious and treatment-related. Each case should include the following: subject and date, description of the event, duration, frequency, degree, severity, actions taken, results and sequelae, and relationship to the tested product.

10.3 Management of serious adverse events

Record of serious adverse events (SAEs) requires an independent table, completed by the investigator for each case.

In addition, serious adverse events were reported to the EC by the investigator through the project leader. Such events should be informed immediately by telephone and the SAE form reported within 48 hours.

After an adverse event occurs, if further information examination is required to evaluate the relationship between the adverse event and the test sample, all tests or laboratory results must be attached to the CRF or follow-up records.

10.4 Subject safeguards

Subjects participating in the clinical trial will be purchased clinical trial liability insurance. All the subjects use adverse events or serious adverse events during the clinical trial, and make economic compensation according to the severity of the adverse event.

11 Ethical requirements

11.1 Protection of subject privacy

The privacy of all participants will be protected and subjects will be identified by an identification code.

11.2 informed consent

The investigator receives written informed consent from each subject before each subject performs enrollment screening. The informed consent form will be signed and dated by the investigator and the subject. The informed consent form is in duplicate: the first remains in the investigator folder and the second to the subject. Testing could not be performed on subjects until written informed consent.

11.3 Approval of the ethics committee

The Investigator is to submit the study protocol to the Institutional Review Board (IRB) / Independent Ethics Committee (IEC) for review. Clinical studies could not be performed without written approval from the ethics committee.

Any additions or changes to the future study protocol will require notification of the IRB / IEC. The IRB / IEC should also be notified if any serious adverse event occurs during the clinical study.

11.4 Declaration of Helsinki

This study will be conducted in accordance with the principles and provisions of the Declaration of Helsinki and the subsidiary articles.

12 Quality control and quality assurance

The implementation process of this trial will refer to the trial protocol, the Good Laboratory Practice for Drug Clinical Trial issued by the State Food and Drug Administration and the NHC (2020 edition), and comply with relevant laws and regulations.

The investigator shall strictly follow the protocol; the hospital will manage and quality control the trial as required; an independent clinical trial monitor (CRA) will monitor the quality of the test; the CRA will monitor and report the project weekly.

13 Study termination

If it is clear that the study is be continued early before the completion of the study, the investigator will notify the Ethics committee of the reason in advance. Data not released / not used in the study, the test samples will be destroyed or returned.
